6.2. Inclusion Criteria

- (1) The subject is a male ≥ 18 years old.
- (2) The subject has had an original diagnosis of PCa and underwent radical curative therapy at least 3 months before enrolment, and has been diagnosed with BCR on the basis of:
 - a. Post RRT / brachytherapy: Increase in PSA level ≥ 2.0 ng/mL above the nadir level after radiotherapy (RT) or brachytherapy (ASTRO-Phoenix criteria) [53], or
 - b. Post RP: EITHER two consecutive rises in PSA and final PSA > 0.1 ng/mL OR three consecutive rises in PSA. This definition is also applicable to subjects with PSA persistence post RP (where the PSA fails to fall to undetectable levels).
 - i. In addition, the subject post RP, should have a PSA doubling time of ≤ 15 months OR PSA level ≥ 1.0 ng/mL at time of recruitment. The PSA doubling time will be calculated using the Memorial Sloan Kettering Cancer Center nomogram (<http://www.mskcc.org/nomograms/prostate/psa-doubling-time>), based on a minimum of two PSA levels within 12 months of screening, taken after the last recorded nadir PSA available at time of screening.
- (3) The subject has not had previous recurrences of PCa, i.e. this is the first diagnosis of BCR.
- (4) The subject is being considered for radical salvage therapy.
- (5) The subject is able and willing to comply with study procedures, and signed, dated and timed informed consent is obtained before any study-related procedure is performed.
- (6) The subject's Eastern Cooperative Oncology Group [ECOG] performance status 0-2.
- (7) The subject should not have received androgen-deprivation therapy within 3 months of screening.
- (8) The subject has a normal or clinically acceptable medical history and vital signs findings at screening (up to 14 days before administration of study drug).

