2 GENERAL PRINCIPLES

The analysis and statistical reporting will be conducted at Syne qua non using SAS version 9.2 or higher.

All listings will be based on all enrolled subjects unless specified otherwise. All tables will be presented by site and overall for the appropriate analysis population.

Descriptive summary statistics for continuous variables will include number of subjects (n), mean, standard deviation (SD), minimum, median, and maximum, unless specified otherwise. The precision of these summary statistics is defined in the table, figure and listing shells document.

Descriptive summary statistics for categorical variables will include frequency counts and percentages [n (%)]. Unless stated otherwise, the denominator for percentage calculations will be the number of subjects in the analysis set.

For treatment response baseline prostate specific antigen (PSA) is the most recent PSA measurement prior to salvage therapy for subjects who had salvage treatment and the most recent PSA measurement prior to the 18F-fluciclovine positron emission tomography/computerised tomography (PET/CT) for non-salvage subjects. If no PSA measurement is available just prior to salvage therapy, baseline will be defined as the most recent PSA measurement prior to fluciclovine (¹⁸F) scan. For all other variables, and for baseline PSA other than for treatment response, baseline is defined as the most recent value prior to fluciclovine (¹⁸F) administration.

In general, there will be no imputation of missing data, however where dates are partially missing dates may be imputed for calculation purposes, details are given under relevant section.

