3.5 Changes from the Protocol Planned Analysis

The protocol specified "Improvement in outcome of radical salvage treatment based on fluciclovine (¹⁸F) PET/CT being included in the assessment" as a secondary endpoint. This was to be assessed based on PSA and radiological response. Due to lack of data being recorded for radiological response this definition was not used, treatment response was instead assessed using PSA only (see section 5.4.2.1.).

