5.4 Statistical Analysis

5.4.1 Primary Efficacy Analysis

The analysis of the primary outcome will be performed on the EAS as the primary analysis and will be repeated on the PPS as a secondary analysis. Comparisons between the original treatment plan and the revised treatment plan will be categorised as no change, major change or other change. The definitions of the change categories are listed below.

- No change: the original treatment plan is the same as the revised treatment plan
- Major change: the original treatment plan is not the same as the revised treatment plan and the grouping for the original treatment plan is not the same as the grouping for the revised treatment plan

These will be further split and presented according to the following categories:

- Salvage or Non-curative systemic therapy to Watchful waiting
- Salvage therapy to Non-curative systemic therapy
- Non-curative systemic therapy to Salvage therapy
- Alternative Major change
- Other change: the original treatment plan is not the same as the revised treatment plan but the grouping for the original treatment plan is the same as the grouping for the revised treatment plan

These will be further split and presented according to the following categories:

- Modified RT field plan
- Modified androgen-deprivation regimen
- Alternative Other change

Groupings of treatment plans are detailed in the following table:

Date: 10OCT2018 Version: Amendment 1 Final

Version: Amendment 1 Fina ST/form/010/6

Original Treatment Plan	Grouping for Original Tx Plan	Revised Treatment	Grouping for Revised Tx Plan
Was androgen deprivation therapy planned	Androgen Deprivation Therapy	Androgen deprivation therapy	Androgen deprivation therapy
		Watch and wait	Watch and wait
		Chemotherapy	Chemotherapy
Salvage radiotherapy to the prostate bed		Salvage radiotherapy to the prostate bed	
Salvage radiotherapy to the prostate bed, with boost to areas guided by conventional imaging	Salvage Radiotherapy	Salvage radiotherapy to the prostate bed, with boost to areas guided by conventional imaging	Salvage Radiotherapy
		Salvage radiotherapy to the prostate bed with boost to areas guided by fluciclovine (18F) PET/CT	
Salvage radiotherapy to the prostate bed and whole pelvis		Salvage radiotherapy to the prostate bed and whole pelvis	

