5.4.2 Secondary Efficacy Analyses

5.4.2.1 Treatment response as assessed by change in PSA

An assessment of treatment response, which is based on the percentage change in PSA from baseline to the last value reported, is defined as:

- >=30% decrease in PSA will be considered to be a response to treatment
- <25% increase or <30% decrease will be classified as stable disease
- >=25% increase in PSA will be classified as disease progression

See section 2 General Principles for baseline definition.

The number, percentage and exact 95% CI of subjects having a treatment response, stable disease and disease progression, as assessed by change in PSA, will be presented overall and separately for subjects in the FAS who had salvage treatment, for subjects who had non-salvage treatment, for those with a change in management plan and for subjects with no change in management plan following the ¹⁸F-fluciclovine PET/CT scan. In addition, treatment response assessed by change in PSA will be summarised by disease location (local disease versus extra-prostatic disease) and treatment administered.

The percentage change in PSA from baseline to the last value reported will be summarised overall and by subjects who had a change in management plan versus those who did not have a change in management plan following the ¹⁸F-fluciclovine PET/CT scan, disease location and treatment administered.

Finally, a waterfall plot of the maximum percentage reduction in PSA during the 4-8 month window will be presented on the y-axis and each subject will be represented by a bar on the x-axis. The bars will be ordered in descending order of the magnitude of the percentage change in PSA value.

Treatment response and the factors used to assess the response will be listed in full.

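### PSA change is the SAP's only measure of treatment response, but the salvage and guided/not-guided response tables pool patients with and without concurrent androgen deprivation

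*SAP*

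**What the plan says.** - **Response measure.** SAP 3.5: "Due to lack of data being recorded for radiological response this definition was not used, treatment response was instead assessed using PSA only". SAP 5.4.2.1 then classifies the percentage PSA change from baseline to the last reported value: ">=30% decrease in PSA will be considered to be a response to treatment". Smaller changes are stable disease, and a rise of 25% or more is progression.
- **Baseline.** SAP 2 takes, for salvage patients, "the most recent PSA measurement prior to salvage therapy", with the last pre-scan value as fallback. ADT status plays no part in the rule.
- **Tables.** SAP 5.4.2.1 gives exact 95% intervals overall, for salvage and non-salvage patients, and "for those with a change in management plan and for subjects with no change in management plan following the" scan. It adds that "treatment response assessed by change in PSA will be summarised by disease location (local disease versus extra-prostatic disease) and treatment administered". The SAP text does not list the treatment-administered categories.
- **Guided/not guided.** Addendum 2 (Change 1, Table 14.2.2.5) divides salvage patients by a text string in the agreed therapy. Its stated reason repeats the secondary objective on improvement in salvage outcome. ADT is not a criterion.
- **ADT in the plan.** The grouping table in SAP 5.4.1 has its own item, "Was androgen deprivation therapy planned", next to the salvage items. A modified ADT regimen is also one of the sub-categories of change. Protocol 6.2 restricts ADT only before entry: the patient "should not have received androgen-deprivation therapy within 3 months of screening".
- **Data.** SAP 4.4.4 lists every prostate cancer therapy with its class and its start and end dates.

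**The concern.** The secondary objective asks about the outcome of radical salvage treatment. With radiological response gone, a fall in PSA is the only evidence of response. ADT lowers PSA through hormone suppression, whatever salvage has achieved. The plan itself accepts a PSA fall as response under non-salvage management (Protocol 7.7, follow-up table). A salvage patient who also receives ADT can therefore be counted as a salvage responder because of the ADT.

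Two readings are at stake. The first is the absolute response rate in the salvage table. The second is the contrast in the guided/not-guided table, which was added specifically to look for better salvage outcome. If ADT use differs between guided and not-guided patients, a difference in response can appear with no difference in what salvage did.

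**Working it through.** **1. Figures in the plan.** The plan states no figure for PSA response or for ADT use. Its one sizing calculation is for the primary endpoint (Protocol 11.1, SAP 3.4): 1.96² × 0.20 × 0.80 / 0.06² = 170.7, so 171; and 171 / 0.95 = 180. Both reproduce, but neither bears on this point.

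**2. Is ADT separated anywhere?**

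| Summary | Where | ADT separated? |
|---|---|---|
| Salvage / non-salvage | SAP 5.4.2.1 | No |
| Change / no change | SAP 5.4.2.1 | No |
| Guided / not guided | Addendum 2 | No |
| Treatment administered | SAP 5.4.2.1 | Categories undefined; not crossed with the rows above |

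**3. Effect on a pooled rate.** Let q be the share on concurrent ADT, pA the response rate with ADT and p0 the rate with salvage alone. All three are assumptions.

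Pooled rate = q·pA + (1 − q)·p0. With pA = 0.95:

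| p0 | q = 10% | q = 30% | q = 50% |
|---|---|---|---|
| 0.30 | 36.5% | 49.5% | 62.5% |
| 0.50 | 54.5% | 63.5% | 72.5% |
| 0.70 | 72.5% | 77.5% | 82.5% |

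The lift over p0 is q(pA − p0). It runs from 0.10 × 0.25 = 2.5 points to 0.50 × 0.65 = 32.5 points.

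**4. Effect on a contrast.** With the same pA and p0 in both groups, the spurious difference is (q1 − q2)(pA − p0). With pA = 0.95:

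| ADT shares | p0 = 0.30 | p0 = 0.50 | p0 = 0.70 |
|---|---|---|---|
| 50% v 30% | 13 points | 9 points | 5 points |
| 60% v 20% | 26 points | 18 points | 10 points |
| 30% v 30% | 0 | 0 | 0 |

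If the two rates lie closer together, the effect shrinks. With pA = 0.80 and p0 = 0.70, shares of 50% v 20% give 0.30 × 0.10 = 3 points, and 40% v 30% give 0.10 × 0.10 = 1 point.

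**5. The opposite direction.** Suppose ADT starts between scan and salvage. Let B be the last PSA before ADT and sB (s < 1) the suppressed value just before salvage. The plan's baseline is sB, so response needs a last PSA of at most 0.70·sB; from B it would need at most 0.70·B. A patient whose last PSA lies between those limits is a responder from B but not under the plan's rule. If this is common, pA can fall below p0 and the sign in step 4 reverses. For example, with pA = 0.50, p0 = 0.70 and shares of 50% v 30%, the difference is 0.20 × (−0.20) = −4 points.

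**The case against.** **Already covered.** SAP 5.4.2.1 summarises response by treatment administered and lists the factors behind each classification. The table shells are a separate document not seen here, and they may already distinguish salvage with ADT from salvage without. This stands in part: a reader might infer that nothing in the plan can separate the two effects, and the documents do not support that. But the SAP text leaves the categories open, and the summary is not crossed with guided status.

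**Co-use is inferred.** The grouping table lists ADT in parallel with salvage and does not say that the two are given together. That is fair. However, ADT is phrased as a separate yes/no item, modified ADT is a kind of change within an unchanged grouping, and nothing restricts ADT after the scan. The entry criterion should not be pressed further: the protocol gives no reason for it, so it does not show that the authors saw ADT as a confounder of response.

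**Assumed size.** Every rate and share above is assumed. This stands.

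**Splitting by ADT has its own problem.** ADT after the scan is a choice that the scan may have influenced, and it can itself be the change in plan. Splitting change/no-change by ADT would condition on part of what is being studied. This stands, and the fix treats that table differently.

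**Secondary and descriptive.** These are untested summaries in a single-arm study. That limits the weight of the point, but the tables still carry confidence intervals and answer a named objective.

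**Conclusion.** The concern holds in a limited form. PSA is the only measure of treatment response, and the salvage and guided/not-guided tables mix patients with and without concurrent ADT. As specified, they cannot isolate salvage response. This rests on two premises: that some salvage patients receive ADT, which the plan's structure makes likely but does not state, and that ADT lowers PSA independently of salvage.

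The size is unknown. Under the assumptions shown with 95% response on ADT, a pooled rate rises by 2.5 to 32.5 points and unequal ADT use produces a false contrast of 5 to 26 points. With closer rates the contrast is 1 to 3 points, with equal shares it is zero, and with early ADT it may reverse.

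Three stronger readings are not supported:

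- That PSA is the trial's only outcome. Management change, detection rate and safety are separate endpoints, and the primary analysis is untouched.
- That the reported response will be inflated. The direction depends on when ADT starts, and no ADT data are given.
- That patients without ADT show the true effect of salvage. They are a selected, non-randomised subset.

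**What to change.** 1. In SAP 5.4.2.1 and Addendum 2 Table 14.2.2.5, present the salvage and guided/not-guided response tables also by ADT (yes/no) between the baseline PSA and the response PSA, derived from the therapy dates in SAP 4.4.4.
2. Define the treatment-administered categories so that salvage with ADT and salvage without ADT are separate.
3. Where ADT began before salvage, add a sensitivity analysis that takes the last PSA before ADT as baseline.
4. For change/no-change, report the number and percentage with ADT in each group rather than rely on a split.
5. State that pooled rates are not to be read as salvage response alone, and that the no-ADT rows are a descriptive, non-randomised, post hoc subset and not a causal estimate.

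**Cost.** A derived flag and extra rows, with no new data collection. Cells will be small, since recruitment stopped after an interim look at 85 evaluable patients (Protocol 11.3). An assumed cell with 8 responders of 15, for instance, has an exact 95% interval of 27% to 79%. Some therapy dates are incomplete and count as concomitant by default (SAP 4.4.4), which blurs the flag. A pre-ADT baseline may fall outside the 31-day pre-therapy window in Protocol 7.7. The split also needs a stated exception to SAP 5.4.5, which rules out subgroup analyses, and it would follow database lock, as Addendum 2 already does.

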5.4.2.2 PSA threshold

The detection rate (DR) will be calculated as number of positive fluciclovine (¹⁸F) scan results/total number of scans.

Date: 10OCT2018 Version: Amendment 1 Final

The point estimate (expressed in percentage) of the DR will be presented at the region level and at the subject level. These rates will be presented for all subjects from the FAS and PPS, overall and across a range of baseline PSA values:

- 0 0.2
- \bullet >0.2 0.5
- \bullet >0.5 1.0
- \bullet >1.0 2.0
- \bullet >2.0 5.0
- \bullet >5.0 10.0
- >10.0

to determine the optimum PSA threshold for lesion detection. See section 2 General Principles for baseline definition.

The detection rates will also be summarised across the following baseline Gleason score categories: <=6, 7, 8 and >=9.

All fluciclovine (18F) and other imaging results will be listed.

Handling of Dropouts or Missing Data 5.4.3

Subjects who withdrew from the study prior to completion will be summarised. Withdrawn subjects will not be directly replaced and no imputation of missing data will be conducted.

5.4.4 **Interim Analyses and Data Monitoring**

A single interim analysis of the primary endpoint will be performed in the first 85 evaluable subjects. If the number of treatment changes is greater than 45 (52.9%, with a 97.5% two-sided CI of 40.3%-62.3%, so the lower limit is over 40%), the trial will be terminated early due to overwhelming effectiveness. If the number of treatment changes is 8 or fewer (9.4%, with a 97.5% two-sided CI of 3.6%-18.9%, so the upper limit in this population is below the 20% of the null hypothesis), the trial will be terminated early due to futility.

Examination of Subgroups

No subgroup analyses will be conducted during the study.

Site Specific Sub-study 5.4.6

A site specific sub-study will be conducted in order to compare the ordered subset expectation maximisation (OSEM) standard of care method of reconstructing PET/CT images with that of the Bayesian penalised likelihood method of PET/CT image reconstruction. The analysis of the sub-study results is beyond the scope of this SAP.

SAFETY EVALUATION

All safety evaluations will be performed on the safety analysis set (SAF) unless specified otherwise.

Date: 10OCT2018 Version: Amendment 1 Final

All safety tables will be presented by centre and overall.

Subjects will be included and counted in summary tables only if they have available data.

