4.4.3 Prostate Cancer History

Details of prostate cancer history will be summarised for subjects from the FAS, and will consist of:

- Time since initial diagnosis (months), calculated as [12*(date of informed consent date of initial prostate cancer diagnosis + 1)/365.25]
- TNM stage: Pathological TNM stage if available, otherwise Clinical TNM stage. A summary for T1 total, T2 total and T3 total will be provided as the sum of the number of subjects in each of the subgroups plus any subjects where only T1, T2 or T3 was recorded.
- Gleason total score: Gleason total score from surgery if available, otherwise Gleason total score from biopsy
- Time since adjuvant treatment (months), calculated as [12*(date of informed consent stop date of adjuvant treatment + 1)/365.25]
- Duration of adjuvant treatment (months), calculated as [12*(stop date of adjuvant treatment – start date of adjuvant treatment + 1)/365.25]

- Time since diagnosis of biochemical recurrence (days), calculated as (date of informed consent – date of diagnosis of biochemical recurrence + 1). Time since diagnosis of BCR may be derived in months if more appropriate.
- Baseline PSA value
- Baseline PSA category (0 0.2, >0.2 0.5, >0.5 1, >1 2, >2 5, >5 10 and >10)

In addition, summary table to summarise baseline Prostate Specific Antigen (PSA) by Prior Radical Prostatectomy status (Prior Radical Prostatectomy vs No Prior Radical Prostatectomy) using descriptive statistics (number of subjects (n), mean, standard deviation (SD), minimum, median, and maximum), will be produced.

Details of prostate cancer history will be listed.

Date imputation for incomplete dates:

- If day part missing, put 15th of the month
- If day and month parts missing, put 01 July

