4.4.4 Cancer Therapies for Prostate Cancer

Cancer therapies for prostate cancer will be coded according to the World Health Organization Drug Dictionary Enhanced (WHO DDE) (Enhanced) version Sep 2015.

Cancer therapies will be categorised as follows:

Subjects with radical prostatectomy:

- Radiotherapy
- No radiotherapy

Subjects without radical prostatectomy:

- Radiotherapy only
 - o EBRT only
 - Brachytherapy only
 - EBRT and brachytherapy
- Radiotherapy and other therapies
 - EBRT and other therapies
 - Brachytherapy and other therapies
- Other therapies

Prior cancer therapies for prostate cancer are defined as those for which the end date is prior to the date of injection of fluciclovine (¹⁸F).

Concomitant/post-scan cancer therapies for prostate cancer are defined as those with a start date on or after the injection date of fluciclovine (¹⁸F), or those with a start date before the injection date of fluciclovine (¹⁸F) but which continued with a stop on or after the injection date of fluciclovine (¹⁸F). Summaries for subjects with prior and post-scan radical prostatectomy will be presented separately.

Date: 10OCT2018 Version: Amendment 1 Final

Summary table to summarise time from ¹⁸F-fluciclovine PET/CT to first post-¹⁸F-fluciclovine treatment in days using descriptive statistics (number of subjects (n), mean, SD, minimum, median, and maximum) will be provided.

If cancer therapy dates are incomplete and it is not clear whether the medication was concomitant, it will be assumed to be concomitant.

The number and percentage of subjects per category of prostate cancer therapy will be presented for all subjects from the SAF, separately for subjects with and without radical prostatectomy. This summary will be repeated for prior and concomitant cancer therapies.

All therapies for prostate cancer will be listed including type of therapy, reported therapy name, medication class, standardised medication name, dose, dose unit, route of administration, start date and end date or 'ongoing' flag, therapy comments.

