The number, percentage and exact 95% CI of subjects with and without a change in management plan after the fluciclovine (18F) scan results become available will be presented. In addition, the number and percentage of subjects with changes categorised as major or other will be presented. These summaries will be repeated separately for subjects with a positive and a negative fluciclovine (18F) scan and for subjects without prostatectomy and with prostatectomy.

Date: 10OCT2018 Version: Amendment 1 Final Page 17 of 22

The number, percentage and 95% CI of subjects who agreed to the revised management plan after fluciclovine (¹⁸F) scan results become available will be presented.

Details of the intended management plan, revised management plan and agreed management plan will be listed.

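### SAP 5.4.2.2 seeks an optimum PSA threshold from pooled detection rates without confidence intervals, across a 2.0 ng/mL cut where the entry rules change the patient mix

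*SAP*

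**What the plan says.** The PSA threshold is the second secondary objective (Protocol 4, SAP 3.1). SAP 5.4.2.2 defines DR as positive scans over all scans and tabulates it in the FAS and PPS, overall and in seven baseline PSA bins cut at 0.2, 0.5, 1.0, 2.0, 5.0 and 10.0 ng/mL. The stated purpose is to find the optimum threshold. The statistic is: "The point estimate (expressed in percentage) of the DR will be presented at the region level and at the subject level". The only further split named there is by Gleason category; SAP 2 adds site for all tables.

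Elsewhere the SAP does more:
- SAP 5.4.1 gives exact 95% intervals for change and no change in management, and repeats the summaries "for subjects without prostatectomy and with prostatectomy".
- SAP 5.4.2.1 plans "The number, percentage and exact 95% CI of subjects having a treatment response".
- SAP 4.4.3 adds a "summary table to summarise baseline Prostate Specific Antigen (PSA) by Prior Radical Prostatectomy status", but that table does not include DR.

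The entry rules in Protocol 6.2 differ by primary treatment:
- After radiotherapy or brachytherapy: "Increase in PSA level ≥ 2.0 ng/mL above the nadir level after radiotherapy (RT) or brachytherapy".
- After prostatectomy: "two consecutive rises in PSA and final PSA > 0.1 ng/mL", or three consecutive rises with no stated PSA floor. In addition, the patient "should have a PSA doubling time of ≤ 15 months OR PSA level ≥ 1.0 ng/mL at time of recruitment".

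SAP 5.4.5 states that subgroup analyses will not be carried out.

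**The concern.** Two features of the plan limit what a threshold read from this table can mean.

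The first is precision. Seven bins divide a modest cohort, and Protocol 11.3 reports that recruitment stopped early after an interim analysis on 85 evaluable patients. Without intervals, the table does not show how much of a difference between neighbouring bins could be chance. Without a criterion for the optimum, two analysts could take different thresholds from the same table and both comply with the SAP.

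The second is composition. The SAP's cut at 2.0 ng/mL falls where the post-radiotherapy entry rule begins to admit patients, so who is in the bin changes together with PSA. A smaller change of the same kind occurs at 1.0 ng/mL, where the doubling-time condition for post-prostatectomy patients ceases to apply. If DR steps up at either cut, the pooled table alone cannot say why.

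At stake is how a secondary result is read and quoted. The primary endpoint is not affected.

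**Working it through.** **1. The plan's own sample size.** SAP 3.4 assumes a 20% rate, a half-width of 6 points and two-sided 95% confidence: n = 1.96² × 0.20 × 0.80 / 0.06² = 170.7, rounded up to 171. With 5% drop-out, 171 / 0.95 = 180. Both figures reproduce. They concern management change in the whole cohort and say nothing about DR by bin.

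**2. Precision per bin.** The documents give neither bin sizes nor the final N, so equal bins are assumed. DR uses the FAS, which contains the evaluable set, so 85 is a floor. The exact (Clopper-Pearson) limits for x of n are the 2.5% quantile of Beta(x, n−x+1) and the 97.5% quantile of Beta(x+1, n−x).

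| N | Per bin | Example | Exact 95% CI | Width (points) |
|---|---|---|---|---|
| 85 | 85/7 = 12.1 | 6/12 | 21.1-78.9% | 57.8 |
| 171 | 171/7 = 24.4 | 12/24 | 29.1-70.9% | 41.8 |

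Real bins will be unequal, so some intervals will be wider and some narrower.

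**3. The protocol's own example.** Protocol 3.3 cites choline PET/CT positivity by PSA band as 3/65, 4/26 and 5/18. The exact 95% intervals are 1.0-12.9%, 4.4-34.9% and 9.7-53.5%. Neighbouring bands overlap.

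**4. Who can be in each bin.** A nadir cannot be negative, so a rise of at least 2.0 above it means PSA of at least 2.0 when recurrence was diagnosed.

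| Baseline PSA (ng/mL) | After radiotherapy or brachytherapy | After prostatectomy |
|---|---|---|
| Below 1.0 | Almost none | Admitted only with doubling time ≤ 15 months |
| 1.0 to 2.0 | Almost none | Admitted whatever the doubling time |
| Above 2.0 | Admitted | Admitted whatever the doubling time |

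The exceptions are marginal: a PSA of exactly 2.0 with a zero nadir, or a last pre-scan PSA lower than the value that established recurrence.

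**5. Scale of a possible mix effect.** Suppose DR did not depend on PSA within either group. The step in pooled DR at 2.0 would then be (radiotherapy share above 2.0) × (DR gap between the groups). For an assumed gap of 10 points and an assumed share of 25% to 75%, that is 2.5 to 7.5 points. With no gap it is zero, and with a negative gap it is negative. The documents give neither quantity.

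**6. Can the table still show a broad gradient?** Take 12 per bin, with four bins up to 2.0 (48 patients) and three above (36). If true DR rises in equal steps from 20% to 80%, the averages on the two sides are 35% and 70%. The chance that the observed pooled DR above 2.0 fails to exceed the one below is about 0.04%. For a rise from 30% to 70% (averages 40% and 63.3%) it is about 1.6%.

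**The case against.** The best defence is that the analysis is descriptive. The objective concerns PSA in relation to scan positivity among men with recurrence, not a causal effect of PSA, and the change of mix at 2.0 comes from the accepted definition of recurrence. That stands: the pooled table correctly describes yield in the enrolled cohort, and a reader who inferred that it is biased or invalid would go beyond the documents.

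A reader might also infer that a threshold below 2.0 would be misapplied to men treated with radiotherapy. This is largely empty. Under the trial's own definition such men have no recurrence until nadir + 2.0, so nearly all of them already exceed any lower threshold at entry.

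Nor do the small bins hide the overall relation. Step 6 shows that a broad rise across 2.0 would be visible even at 12 per bin. The weakness lies in choosing a particular cut, not in seeing a trend.

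The contrast with the rest of the SAP has limits too. SAP 5.4.1 gives only counts and percentages for major and other changes, and SAP 5.4.2.1 does not explicitly promise intervals for its breakdown by disease location. If counts are printed beside each DR, as SAP 2 prescribes for categorical summaries, readers could derive the intervals themselves.

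Finally, SAP 5.4.5 appears to rule out the split proposed here. Yet SAP 5.4.1 already splits the primary endpoint by prostatectomy and scan result, and 5.4.2.2 splits DR by Gleason score. The sentence needs reconciling with the SAP as it stands.

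What remains is that the stated purpose is to determine a threshold, and the plan gives that threshold neither a measure of uncertainty nor a rule for choosing it.

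**Conclusion.** The point holds as a limited one about a secondary analysis. Point estimates alone, in bins of perhaps 12 to 24 patients with 95% intervals some 42 to 58 points wide at a DR of 50%, are a weak basis for an optimum threshold. These widths assume equal bins and a final N between 85 and 171; the final N is not stated.

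The change of mix at 2.0 follows directly from the entry rules and is nearly complete. Whether it moves DR is a different question. That depends on DR differing between the two treatment groups, on which the documents give no figures, so the effect may be zero. A reader might conclude that the threshold should rest on post-prostatectomy patients alone. The documents do not require this: the objective covers all patients with recurrence, and no passage shows how many post-prostatectomy patients lie above 2.0.

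Addendum 1 and the table shells are not in the supplied text, so either may already contain intervals or a split. The text of Addendum 2 that is supplied leaves SAP 5.4.2.2 unchanged.

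**What to change.** In SAP 5.4.2.2:

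1. Keep the pooled table as descriptive and add an exact 95% confidence interval to every DR, at subject and region level.
2. Repeat the DR-by-PSA table by prior prostatectomy (yes/no), as SAP 5.4.1 does for the primary endpoint. Amend SAP 5.4.5 so that it agrees with this and with the splits already planned. State how many in the SAP 4.4.4 category "Subjects with radical prostatectomy" also had radiotherapy, since a yes/no split does not separate them.
3. Report any threshold with its intervals, the criterion used to call it optimum, and the treatment mix of the bins it rests on. Note the changes of entry rule at 1.0 and 2.0 ng/mL.

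The cost is intervals in one planned table and one repeat of it, using data already collected and methods the SAP already uses. The downside is smaller cells: a 12-patient bin split evenly leaves 6, and 3/6 has an exact 95% interval of 11.8-88.2%. Anything added after database lock should be labelled post hoc; Addendum 2 already documents analyses added at that stage.
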